11.3. Tertiary endpoints

- Specific anti-S. sonnei LPS sIgA antibody concentration in stool samples at Day 1, 7 days after first and second vaccination and 7 days after challenge (Day 64).
- Frequency of *S. sonnei* LPS specific IgG α4β7+/- antibody secreting cells per 10⁶ PBMC plasmablast at Day 1 and 7 days after first and second vaccination and 7 days after challenge (Day 8, Day 36 and Day 64). (*Amended: 23 July 2019*)
- Glycosylation profiles of IgG antibodies at Day 1 and 28 days after second vaccination (Visit 5; *Day 57*).
- Number and percentage of subjects that show correlation between serum anti-*S. sonnei* LPS IgG concentration, SBA titer, shigellosis, shedding, MSD, dysentery and mild diarrhea after challenge.
- Concentration of stool markers of intestinal inflammation (e.g. calprotectin and myeloperoxidase) before oral challenge with *S. sonnei*, 53G at Visit 5 (Day 57) and daily during the post-challenge inpatient stay (Day 57 to Day 64).
- The number of differential expressed genes 7 days after first and second vaccination and 7 days after challenge by comparing the relative abundance of mRNA sequences compared to Day 1 (pre-vaccination baseline).
- Diversity and frequency of microbiome components (taxa and/or genes according to technology) at Day 1 prior to vaccination and 28 days after second vaccination (Visit 5; Day 57).

Exploratory analysis for hypotheses generation will include the evaluation of the association of the microbiome components with efficacy and immunogenicity described above.

205626 (S SONNEI MONO GMMA SBVGH-003 [H03_03TP])
Protocol Amendment 6 Final

11.4. Determination of sample size

Primary objective - Efficacy

In comparing the protective efficacy of 1790GAHB vaccine against the placebo group the following assumptions will be made:

Assuming a true VE of 70%, a total number of 21 confirmed cases will be needed to demonstrate that the LL of the two-sided 90% CI for the VE is above 0% with 80% power (by Pass 2013, One Proportion Power Analysis, one-sided test, one-sided alpha = 5%).

Based on the results obtained by the Cincinnati Children's Hospital Medical Center, where the challenge model was developed, in subjects receiving a challenge with 1500 CFU of *S. sonnei* 53G, the attack rate for the primary case definition of this study is 58%. Thus considering an AR of 58% in the placebo group and a percentage of non-evaluable subjects of 22%, approximately 72 subjects (36 per group) will be recruited to reach these 21 cases.

The assumption on the value of true VE is based on the percentage of subjects with seroresponse observed in previous studies where the 1.5/25 µg OAg/protein dose of 1790GAHB vaccine was evaluated. In the phase I study in Europe, the observed percentage of subjects with seroresponse was 63% and 88% after 1st and 2nd vaccination respectively. In the Phase IIa study, conducted in endemic region, the observed percentage of subjects with seroresponse was 68% and 90% after 1st and 2nd vaccination, respectively.

11.5. Analysis sets

11.5.1. All Enrolled Set

All screened subjects who provide informed consent, and provide demographic and/or baseline screening assessments, regardless of the subject's randomization and treatment status in the study and received a Subject ID.

11.5.2. All Exposed Set

All subjects in the enrolled set who receive a study vaccination.

11.5.3. Safety set

11.5.3.1. Solicited Safety Set (solicited local and systemic adverse events and other solicited adverse events)

All subjects in the Exposed Set with any solicited AE data and/or indicators of solicited AEs.

205626 (S SONNEI MONO GMMA SBVGH-003 [H03_03TP])
Protocol Amendment 6 Final

11.5.3.2. Unsolicited Safety Set (unsolicited adverse events)

All subjects in the Exposed Set with unsolicited AE data.

11.5.3.3. Overall safety set

All subjects who are in the Solicited Safety Set and/or Unsolicited Safety Set.

Subjects will be analyzed as "treated" (i.e., according to the vaccine* a subject received, rather than the vaccine* to which the subject may have been randomized).

*Vaccine refers to study vaccine or placebo.

11.5.4. Full analysis set (FAS) efficacy/Immunogenicity set

11.5.4.1. Full analysis set efficacy

All subjects in the All Enrolled Set who are randomized, receive a study vaccination and provide efficacy data.

11.5.4.2. Full analysis set Immunogenicity

All subjects in the All Enrolled Set who are randomized, receive at least one study vaccination and provide immunogenicity data at the relevant timepoints.

In case of vaccination error, subjects in the FAS sets will be analyzed "as randomized" (i.e., according to the vaccine* a subject was designated to receive, which may be different from the vaccine* the subject actually received).

*Vaccine refers to study vaccine or placebo.

11.5.5. Per-protocol (PP) set for efficacy/Immunogenicity set

All subjects in the FAS Efficacy / Immunogenicity who:

- Correctly receive the vaccine* (i.e., receive the vaccine* to which the subjects is randomized and at the scheduled timepoints).
 - *Vaccine refers to study vaccine or placebo.
- Have no protocol deviations leading to exclusion as defined prior to unblinding / analysis.
- Are not excluded due to other reasons defined prior to unblinding or analysis.

PPS are subsets of FAS and should be always defined even if the objectives do not require it.

Examples for subjects excluded due to other reasons than protocol deviations are:

• Subjects who withdrew informed consent.

The primary analysis will be based on the PP cohort for efficacy and immunogenicity. However efficacy and immunogenicity analyses will be performed on both FAS and PP sets.

205626 (S SONNEI MONO GMMA SBVGH-003 [H03_03TP])
Protocol Amendment 6 Final

11.5.6. Other analysis sets

There are no additional analysis sets for analysis in this study.

All subjects who are screened, i.e., consented but not yet randomized/enrolled.

11.5.7. Sub-groups

The analysis for the primary efficacy endpoint will be repeated for the two subgroups of subjects who were responders or non-responders at the immunogenicity assessment of the pre-challenge visit.

11.6. Derived and transformed data

- Screening (anti S. sonnei LPS IgG Screening-ELISA)
 - The cut-off value for the anti *S. sonnei* LPS IgG Screening-ELISA is defined by the laboratory.
 - A seronegative subject is a subject whose titer is below the cut-off value.
 - A seropositive subject is a subject whose titer is greater than or equal to the cutoff value.
- Immunogenicity (anti *S. sonnei* LPS IgG-ELISA):
 - The cut-off value for the anti *S. sonnei LPS* IgG-ELISA is defined by the laboratory.

Seroresponse is aimed to define a significant increase in anti *S. sonnei* LPS IgG concentration in post-vaccination samples and relies on the definition already used in a previous phase II study in Kenyan population. For the purpose of this study seroresponse is defined as:

- If the baseline value is greater than 50 EU/mL then an increase of at least 50% in the post-vaccination sample as compared to baseline.
- If the baseline value is less or equal to 50 EU/mL then an increase of at least
 25 EU/mL in the post-vaccination sample as compared to baseline.

Note: Threshold values/increases given in the definition of seroresponse might be subject to change during the course of the study (e.g., in case of optimization/qualification/validation of the anti *S. sonnei* LPS IgG ELISA).

- The GMC calculations are performed by taking the anti-log of the mean of the log concentration transformations. Values to be used for the antibody concentrations below the assay cut-off will be described in the Statistical Analysis Plan (SAP).
- Handling of missing data: for a given subject and a given immunogenicity measurement, missing or non-evaluable measurements will not be replaced.

205626 (S SONNEI MONO GMMA SBVGH-003 [H03_03TP])
Protocol Amendment 6 Final

- Reactogenicity and safety:
 - Handling of missing data: subjects who missed reporting symptoms
 (solicited/unsolicited or concomitant medications) will be treated as subjects
 without symptoms (solicited/unsolicited or concomitant medications,
 respectively). In case of significant non-compliance of study procedures for
 reporting symptoms, the analysis plan will be reassessed to ensure more accurate
 reporting of study data by further analysis.
 - For the analysis of solicited symptom, missing or non-evaluable measurements will not be replaced. Therefore, the analysis of the solicited symptoms based on the All Enrolled Set will include only subjects/doses with documented safety data (i.e., symptom screen completed).

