11.10. Analysis of safety

The primary analysis will be performed on the All Exposed Set.

Analysis of solicited local and systemic adverse events and other reactions:

Solicited AEs will be summarized according to defined severity grading scales.

Frequencies and percentages of subjects experiencing each AE will be presented for each symptom severity. Summary tables showing the occurrence of any local or systemic AE overall and at each timepoint will also be presented.

Post-vaccination/challenge solicited AE reported from Day 1 to 7 days post-vaccination/challenge will be summarized by maximal severity and by vaccine/placebo group. The severity of solicited local AE will be summarized according to categories based on linear measurement.

Injection-site pain and systemic reactions occurring up to 7 days after each vaccination will be summarized according to "mild", "moderate" or "severe".

Each solicited local and systemic AE will also be further summarized as "none" versus "any".

Analysis of unsolicited AEs:

All the AEs occurring during the study, judged either as probably related, possibly related, or not related to vaccination/challenge by the investigator, will be recorded.

The original verbatim terms used by investigators to identify AEs in the eCRFs will be mapped to preferred terms using the MedDRA dictionary. The AEs will then be grouped by MedDRA preferred terms into frequency tables according to system organ class. All reported AEs, as well as AEs judged by the investigator as at least possibly related to study vaccine/placebo or challenge agent, will be summarized according to system organ class and preferred term within system organ class. These summaries will be presented by vaccination group. When an AE occurs more than once for a subject, the maximal severity and strongest relationship to the vaccine/placebo group will be counted.

Separate summaries will be produced for the following categories:

- SAEs.
- AEs that are possibly or probably related to vaccine/placebo or challenge agent.
- AEs leading to withdrawal from the study.

Data listings of all AEs will be provided by subject. In addition, AEs in the categories above will be provided as listed data.

205626 (S SONNEI MONO GMMA SBVGH-003 [H03_03TP])
Protocol Amendment 6 Final

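### Section 11.6 gives two incompatible rules for missing post-vaccination solicited adverse event data, and Section 11.10 leaves the denominator unsettled between subjects with documented data and all exposed subjects

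*Protocol*

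**What the plan says.** Two bullets under reactogenicity and safety in Protocol Section 11.6 deal with missing data.

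- **First rule.** It opens "Handling of missing data: subjects who missed reporting symptoms" and continues, in brackets, "solicited/unsolicited or concomitant medications) will be treated as subjects" without symptoms. The bracketed list appears twice in the sentence, and solicited symptoms are in it both times. The analysis plan is to be reassessed if non-compliance with symptom reporting is significant. That term is not defined.
- **Second rule.** "For the analysis of solicited symptom, missing or non-evaluable measurements" are not replaced. It follows, according to the bullet, that "the analysis of the solicited symptoms based on the All Enrolled Set will include only subjects/doses with documented safety data", which is explained as a completed symptom screen.

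The analysis sets are named elsewhere:

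- Section 11.5.1 defines the All Enrolled Set as "All screened subjects who provide informed consent, and provide demographic and/or baseline screening assessments", whatever their randomization or treatment status.
- Section 11.5.3.1 defines the Solicited Safety Set: "All subjects in the Exposed Set with any solicited AE data and/or indicators of solicited AEs".
- Section 11.10 opens the safety analysis with "The primary analysis will be performed on the All Exposed Set" and turns at once to solicited events. Section 11.5.2 defines that set by receipt of a study vaccination, with no requirement for data.

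Section 12.2 requires blank or illegible diary fields to be entered as missing in the eCRF.

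**The concern.** Take a vaccinated subject who returns no diary for a dose. Under the first rule this subject stays in the denominator as symptom-free. Under the second rule the subject leaves the analysis of that dose. These are different percentages from the same data, and the protocol does not say which to report.

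Solicited events within 7 days after each vaccination are a secondary safety endpoint (Section 11.2), with only 36 subjects planned per arm, so a few missing diaries move a percentage visibly. The first rule takes the most favourable value for every missing subject. If diary return differs by arm, it also changes the apparent difference between vaccine and placebo.

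This is not detail left to the SAP. The protocol states both rules and names the sets. An SAP that picks one rule departs from the other, and Section 11.12 requires departures from the protocol's statistical plan to be described and justified.

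**Working it through.** **Reading the passages together.** The first rule includes solicited symptoms and assigns absence of symptoms. The second concerns solicited symptoms only and forbids replacement. Section 12.2 records a blank as missing, which fits the second rule and not the first.

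**Which denominators really differ.** Never-vaccinated subjects are in the All Enrolled Set, but they have no post-vaccination symptom screen. Once that set is limited to documented data, it largely coincides with the Solicited Safety Set. One distinction remains: Section 11.5.3.1 admits a subject with any solicited data, whereas Section 11.6 works by subject and dose. A subject with a diary for dose 1 only is in the Solicited Safety Set but should not count in the dose 2 denominator. The substantive conflict is therefore documented-data subjects (Sections 11.6 and 11.5.3.1) against all exposed subjects (Section 11.10).

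**Size of the effect.** The protocol gives no diary non-return rate and no expected reactogenicity rate, so there is no stated figure to reproduce. The only input from the document is n = 36 planned per arm (Section 11.4). The missing counts m and all symptom rates below are assumptions.

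With x documented cases:

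- second rule: x/(n − m)
- first rule on the All Exposed Set: x/n
- ratio of first to second: (n − m)/n

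| m of 36 | Second rule | First rule | Ratio |
|---|---|---|---|
| 2 | 17/34 = 50.0% | 17/36 = 47.2% | 0.944 |
| 4 | 16/32 = 50.0% | 16/36 = 44.4% | 0.889 |
| 8 | 14/28 = 50.0% | 14/36 = 38.9% | 0.778 |

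The shift in points grows with the rate. At an assumed 80% and m = 4, the first rule gives 0.80 × 32/36 = 71.1%, about 9 points lower.

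**Relation to the true rate.** With m = 4 and x = 16, the true proportion among the 36 lies between 16/36 = 44.4% (no missing subject had the symptom) and 20/36 = 55.6% (all four had it). The first rule always reports the lower end.

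**Between-arm difference.** Assume documented rates of 50% (vaccine) and 20% (placebo), a difference of 30 points. Under the first rule:

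- 4 missing in each arm: (0.5 × 32 − 0.2 × 32)/36 = 9.6/36 = 26.7 points
- 8 missing on vaccine, 2 on placebo: (0.5 × 28 − 0.2 × 34)/36 = 7.2/36 = 20.0 points
- 2 missing on vaccine, 8 on placebo: (0.5 × 34 − 0.2 × 28)/36 = 11.4/36 = 31.7 points

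So the distortion can go either way, depending on which arm has more missing diaries.

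**The case against.** The best defence is that the two rules can be read together. The second is the specific rule for solicited symptoms and should govern. The first would then apply to an item left unreported on a completed screen, while a dose with no completed screen drops out. On that reading an unreturned diary never becomes a symptom-free subject. The reading is sensible, but the text does not give it. The first rule speaks of subjects who missed reporting, not of items on a completed form, and it names solicited symptoms. Nor does it fit Section 12.2, where a blank field is missing.

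Several parts of the defence do stand:

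- The lower rate arises only if diary data are missing and the first rule is applied over the second.
- Missing diaries may be few. Section 6.6.14.2.1 schedules reminder calls on Days 3, 7, 31 and 35, and diaries are returned at Visits 2 and 4. The trial is observer-blind, so a large imbalance between arms is not to be expected.
- After challenge, the investigator records events during the inpatient stay (Section 9.1.3.3), so only post-vaccination reactogenicity is exposed.
- The reassessment clause is some protection, but without a threshold or timing the rule could be changed after the data are seen.
- Section 11.11 makes these comparisons descriptive.

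A reader might infer two stronger things. One is that screen failures would dilute the rates through the All Enrolled Set. The limit to documented data prevents that. The other is that three numerically different denominators compete. Three sets are named, but in effect the choice is between two.

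**Conclusion.** The contradiction is real and is in the current text: Section 11.6 both assigns absence of symptoms to subjects with missing solicited reports and forbids replacing missing solicited data. The denominator is unsettled between documented-data subjects and all exposed subjects, and the All Enrolled Set is a wrong label with little practical effect.

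Under the first rule on the All Exposed Set, rates fall by the factor (n − m)/n. With 2 to 8 of 36 missing, an assumed 50% is reported as 47.2% to 38.9%. These sizes rest on assumed missing counts and assumed symptom rates. The documents do not support a statement that reactogenicity will be understated, only that the first rule allows it.

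The primary efficacy analysis is untouched. This is a minor to moderate point that should be corrected because the correction is easy.

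**What to change.** 1. In the first rule of Section 11.6, delete the word solicited both times it occurs, so that no report means no event only for unsolicited adverse events and concomitant medications.
2. In the second rule, replace the All Enrolled Set with the Solicited Safety Set, analysed as treated. For each dose, use subjects with documented data for that dose as the denominator, without imputation.
3. In Section 11.10, say that the All Exposed Set applies to unsolicited adverse events and SAEs. Reconcile this with Section 11.5.3.2, whose Unsolicited Safety Set is limited to exposed subjects with unsolicited AE data; otherwise the same kind of inconsistency remains there.
4. Report the number of missing diaries by arm and dose.

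The cost is a few sentences in Sections 11.6, 11.10 and 11.5.3.2, plus one row of counts in the reactogenicity tables. No new data are needed.

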
11.7. Analysis of demographics

Descriptive statistics (mean, standard deviation, median, minimum and maximum) for age, height and weight at enrolment will be calculated overall and by vaccine/placebo group.

Distributions of subjects by gender and geographic ancestry will be summarized.

11.8. Analysis of efficacy

VE will be evaluated at the end of study period. VE will be estimated as 1-RR where RR is the risk ratio (proportion of subjects reporting the disease in the vaccinated group over the proportion in the placebo group) together with 90% CIs.

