1.2.2. Rationale for the study design

A human challenge model of *S. sonnei* disease for vaccine testing was established in Thailand [Bodhidatta, 2012] and showed an attack rate (AR) of 75% in non-immune adult volunteers receiving a challenge dose of 1680 colony forming units (CFU) of *S. sonnei* strain 53G. Clinical and laboratory endpoints of infection and disease, namely diarrhea, dysentery, fever and shedding of *S. sonnei* in stools were used to calculate the AR and thus to establish the optimal infective dose. In a subsequent study though [Pitisuttithum, 2016], the AR in the control group, using this model, was much less than previously published.

Given this variability, before starting a vaccine-challenge study, the proposed human challenge model of *S. sonnei* to be used has been appropriately developed and the challenge dose and AR reliably established by the Cincinnati Children's Hospital Medical Center (CCHMC) (Ohio, United States of America). The current GSK vaccine-human challenge study will be conducted at CCHMC and will use the developed challenge model. Volunteers will be treated after development of symptoms of shigellosis.

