3.2. Challenge Phase

Four weeks after completion of the two-dose vaccination schedule (approximately 28 days after Visit 3) subjects will be admitted the day before the challenge date (Day 56) and will stay for 9 days in the inpatient unit. Biological sample collection could start for logistical reason at Day 56 (the day of admission before challenge). The day of challenge (Visit 5; Day 57), they will be administered a 1500 CFU challenge dose of *S. sonnei* 53G. Before receiving the challenge, all inclusion and exclusion criteria and hematology will be assessed.

When assessing inclusion and exclusion criteria, the investigator will also inquire about antibiotic treatment during the week prior to the challenge date. Any subject who had a course of antibiotic the week prior to challenge, will not receive the challenge agent.

Subjects will fast for 90 minutes prior to receiving the *S. sonnei* 53G challenge inoculum and an additional 90 minutes after challenge. All subjects in the same cohort will be challenged in the same day using the same inoculum, which will ensure the consistency of the dose used. Approximately 5 minutes before drinking the challenge suspension, the subject will drink a 120 mL solution of sodium bicarbonate to neutralize gastric acidity. A subject with fever or signs of acute illness will not receive the challenge agent and any subject who vomits following ingestion of the challenge agent will not be re-dosed. A note will be made in the subject source documents regarding the apparent amount of the vomitus (small, moderate or large). The subject will still continue in the study and undergo all study-related procedures. Care will be taken to ensure that a minimum amount of time, not to exceed 2 hours, is spent between the reconstitution of the challenge inoculum and the oral administration of the inoculum to the subject.

Two mL of the inoculum will be retained for pre- and post-challenge quantification of the dose. Aliquots of the retained inoculum will be streaked onto trypticase soy agar (TSA) plates and after incubation, average number of colonies on the TSA plates will be counted and CFU/mL will be calculated. Study staff will take all necessary precaution needed for handling of *S. sonnei* 53G and adhere to the CCHMC policy and procedures.

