6.2.2.2.1. Study group and treatment number allocation

The target will be to enroll approximately 72 eligible subjects who will be randomly assigned to two study groups in a 1:1 ratio (approximately 36 subjects in each group).

205626 (S SONNEI MONO GMMA SBVGH-003 [H03_03TP]) Protocol Amendment 6 Final

Subjects will be enrolled in 4 overlapping cohorts of 18 subjects each, for logistical reasons at the clinical site, therefore a 1:1 ratio should be maintained at the cohort level. However, if for any reason, a cohort does not reach the planned 18 subjects, additional subjects can be added in the next cohorts. The maximum number of subjects must not be more than 20 (maximum number of beds in the clinic) in each cohort.

Allocation of the subject to a study group at the investigator site will be performed using the Source DataBase for Internet Randomization system (SBIR). The randomization algorithm might use a minimization procedure; more details are provided in the Statistical Analysis Plan.

After obtaining the signed and dated ICF from the subject and having checked the eligibility of the subject, the site staff in charge of the vaccine/placebo administration will access SBIR. Upon providing the subject identification number, the randomization system will determine the study group and will provide the treatment number to be used for each dose.

A randomization blocking scheme (1:1 ratio) will be used to ensure the balance between treatments is maintained, accounting also for the enrolment cohorts: same number of vaccine and control recipients in each cohort.

The number of each administered treatment must be recorded in the eCRF on the Vaccine Administration screen.

When SBIR is not available, please refer to the SBIR user guide or the Study Procedures Manual (SPM) for specific instructions.

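### Section 11.8 defines VE from pooled arm proportions although randomisation and challenge are organised by cohort; stratifying by cohort would be a small gain in precision

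*Protocol*

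**What the plan says.** - **Estimator.** Protocol Section 11.8: "VE will be estimated as 1-RR where RR is the risk ratio". The ratio is the diseased proportion in the vaccine arm over that in the placebo arm, reported with 90% CIs. No cohort term, stratification or interval method is named. Section 2.1 makes the lower limit of this interval the success criterion.
- **Randomisation.** Section 6.2.2.2.1 describes a 1:1 blocking scheme, "accounting also for the enrolment cohorts: same number of vaccine and control recipients in each cohort". Section 3 plans four cohorts of 18.
- **Challenge.** Section 3.2: "All subjects in the same cohort will be challenged in the same day using the same inoculum". Inoculum is retained so that the dose can be quantified before and after challenge.
- **Attack rate.** Section 1.2.2 cites 75% in the first study of the model and says that the control-group rate in a later study "was much less than previously published". It adds that dose and attack rate have since been reliably established at the study site.
- **Sample size.** Section 11.4: "Assuming a true VE of 70%, a total number of 21 confirmed cases will be needed" to show that the lower limit of the "two-sided 90% CI for the VE is above 0% with 80% power". The placebo attack rate is 58% and 22% are expected to be non-evaluable.

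**The concern.** Cohort is both a randomisation stratum and the unit that shares an inoculum, so it may predict outcome. Balanced allocation removes between-cohort differences from the comparison of arms. A binomial variance computed from the pooled proportions still contains them, because the pooled p(1−p) exceeds the average within-cohort p(1−p) whenever cohort rates differ. The interval that decides the trial would then be wider than the sampling variation that the design leaves, and precision already secured by the randomisation would go unused.

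**Working it through.** **1. The plan's own figures.** With VE 70% and equal arms, the vaccine share of cases is 0.3/1.3 = 0.231. An exact one-sided 5% binomial test on 21 cases rejects at 6 or fewer vaccine cases: alpha 3.9%, power 80.8%. Evaluable subjects per arm: 21/(0.58 × 1.3) = 27.9. Dividing by 0.78 and rounding up gives 36 per arm, 72 in total. Both stated figures reproduce.

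**2. Set-up for the check.** About 28 evaluable per arm is 7 per arm per cohort. The cohort attack rates are assumed, always with mean 58%, and RR is common to all cohorts.

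**3. Point estimate.** With equal arm sizes in every cohort, the Mantel-Haenszel weights are identical in numerator and denominator, so the stratified RR equals the crude RR. Only the interval changes.

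**4. Variance of log RR**, with n = 28, m = 7, cohort placebo rates p_k, q_k = RR·p_k, and pooled p and q:

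- Crude: (1−p)/(np) + (1−q)/(nq)
- Under cohort balance: Σm·p_k(1−p_k)/(Σm·p_k)² + Σm·q_k(1−q_k)/(Σm·q_k)²

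Example: rates 28/48/68/88%, RR 0.3.

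- Crude: 0.42/16.24 + 0.826/4.872 = 0.0259 + 0.1695 = 0.1954; SE 0.442.
- Balanced: 5.421/263.7 + 3.898/23.74 = 0.0206 + 0.1642 = 0.1848; SE 0.430.
- Ratio: 1.028.
- Expected lower limit of VE: 1 − 0.3·exp(1.645 × 0.442) = 37.9% crude; 39.2% with the balanced SE.

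Crude SE divided by balanced SE:

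| Assumed cohort rates | VE 70% | VE 50% | VE 0 |
|---|---|---|---|
| all 58% | 1.000 | 1.000 | 1.000 |
| 48–68% | 1.003 | 1.005 | 1.011 |
| 38–78% | 1.012 | 1.022 | 1.050 |
| 28–88% | 1.028 | 1.050 | 1.122 |
| 20–95% | 1.046 | 1.084 | 1.218 |

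**5. Simulation**, 200,000 trials per scenario, 7 per arm per cohort. Crude log-RR Wald interval against Mantel-Haenszel RR with Greenland-Robins variance, two-sided 90%:

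| Assumed cohort rates | One-sided error | Power, VE 50% | Power, VE 70% |
|---|---|---|---|
| 38–78% | 3.4% vs 4.7% | 68.7% vs 71.6% | 94.0% vs 95.0% |
| 28–88% | 2.5% vs 4.7% | 69.3% vs 75.1% | 94.6% vs 96.2% |

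With all rates at 58%, the error is 4.2% vs 4.5%, so a little of the conservatism is a small-sample effect unrelated to cohorts. Power at VE 70% sits near 94% rather than 80% because two proportions are compared with 28 per arm (about 95% by the usual formula), while Section 11.4 uses the fixed-case binomial test.

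**6. Imperfect balance.** When 22% of 9 per arm per cohort drop out at random, the direction holds but the gain shrinks. The error is 4.0% vs 4.7% at 38–78%. Power at VE 50% is 70.3% vs 71.6% (38–78%) and 70.8% vs 74.3% (28–88%). With equal or mildly spread rates there is no gain, and stratifying can cost up to about 0.5 power points.

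**The case against.** The strongest objection is that Section 11.8 does not settle what is criticised. It gives no interval method, and under exact balance its RR already equals the Mantel-Haenszel RR. Interval method and stratification are commonly left to the SAP, which is not at hand. This stands in part: the absence of an interval method is no fault here. But Section 11.8 writes the estimator out from pooled proportions and defers nothing, whereas Sections 6.2.2.2.1 and 11.6 refer to the SAP explicitly. Section 11.12 asks that any change from the plan outlined in the protocol be described and justified in the final report.

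A second objection concerns the premise. A reader might infer from Section 1.2.2 that attack rates in this trial are known to vary widely between cohorts. The text does not say that. It compares two earlier studies, gives no figure for the second, and says the rate has since been established at this site. All cohorts share one site, one strain and a nominal 1500 CFU. Separate inocula make some spread plausible, but its size is assumed. This objection stands.

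Third, stratifying is not free in every case. With mild spread (48–68%) and VE 70%, the median Greenland-Robins interval is slightly wider than the crude one (log width 1.464 vs 1.454). It would therefore be wrong to say that the crude interval is too wide in every trial where cohort rates differ.

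**Conclusion.** The point holds as a minor improvement in precision. If cohort attack rates differ, a 90% CI from the pooled proportions is conservative. For assumed spreads of 38–78% and 28–88%, one-sided error is 3.4% and 2.5%, against 4.7% with stratification. The power gain is about 0–1.5 points at the design VE of 70%. It is about 3–6 points at VE 50% with balanced cohorts and moderate to large spread, and less when random non-evaluability breaks the balance. These sizes depend on the assumed spread and a common RR.

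A reader might infer that the primary analysis is invalid, biased or underpowered. The documents do not support that: error stays below 5%, the point estimate is unchanged under exact balance, and the stated 21 cases, 72 subjects and 80% power all reproduce.

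**What to change.** In Section 11.8, define VE as 1 minus the Mantel-Haenszel risk ratio stratified by enrolment/challenge cohort, with a cohort-stratified 90% CI (for example stratified Miettinen-Nurminen, or Greenland-Robins) as the interval for the primary criterion. Keep the crude risk ratio as a sensitivity analysis, and settle the choice before unblinding. The simulated figures above are for Greenland-Robins; the Miettinen-Nurminen interval was not simulated.

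The cost is one or two sentences and no new data, since cohort is already part of the allocation. The downside is the possible loss of up to about 0.5 power points noted above if cohort attack rates turn out nearly equal.
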